10.2.1.1 Incidence Rate of TEAE in the First Week of Study Treatment

Number and percent of subjects experiencing TEAEs will be summarized for the first week of study treatment (Day 1 to Week 1 visit, inclusive), for resected population and non-resected population. Specifically, TEAEs will be summarized by treatment group as described below:

- 1. An overview of the number and percentage of subjects with TEAEs in the first week
- 2. A summary of the number and percentage of subjects with TEAEs in descending order of overall incidence frequency by MedDRA PT in the first week
- 3. A summary of the number and percentage of subjects with TEAEs by primary MedDRA SOC and PT in the first week
- 4. A summary of the number and percentage of subjects with serious TEAEs in descending order of overall incidence frequency by MedDRA PT in the first week
- 5. A summary of the number and percentage of subjects with serious TEAEs by primary MedDRA SOC and PT TEAEs in the first week
- 6. A summary of the number and percentage of subjects with TEAEs leading to discontinuation of study drug by primary MedDRA SOC and PT in the first week
- A summary of the number and percentage of subjects with drug-related (i.e., with reasonable possibility to be related to study drug) TEAEs by primary MedDRA SOC and PT in the first week
- 8. A summary of the number and percentage of subjects with TEAEs by primary MedDRA SOC, PT and maximum severity in the first week

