## 5.3 Prohibited Medications and Therapy

---

In addition to the medications listed in the eligibility criteria, use of non-CREON® pancreatic enzyme supplementation or over-the-counter supplements that contain lipase, protease, and amylase as active ingredients, other than the study drug, is prohibited during the treatment period until the last dose of study drug.

Subjects in Screening, who are washing out of PERT, may resume PERT after collecting Stool specimen for Sudan stain test until 1 week prior to Day 1.

**For resected subjects:** Subjects must not have started chemotherapy or radiation therapy from the time of the resection until after Week 1 of the study. However, neoadjuvant therapy prior to the resection is allowed.

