## 4.2 Recording Data and Analyses of Safety Findings

---

Adverse events will be coded using the Medical Dictionary for Regulatory Activities (MedDRA). The number and percentage of subjects with treatment-emergent adverse events (i.e., any event that begins or worsens in severity after initiation of study drug through 30 days post-study drug dosing) will be tabulated by primary MedDRA system organ class (SOC) and preferred term (PT). The tabulation of the number of subjects with treatment-emergent adverse events by severity grade and relationship to study drug also will be provided. Subjects reporting more than 1 adverse event for a given MedDRA preferred term will be counted only once for that term using the most severe grade according to the severity grade table and the most related according to the relationship to study drug tables. Subjects reporting more than 1 type of event within an SOC will be counted only once for that SOC.

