4.2 Analysis Treatment Groups for Various Analyses

Table 1.Analysis Population and Analysis Treatment Groups for Various
Analyses

		R	esected	Non- Resected (All High Dose)
Analysis	Analysis Set	Analysis Treatment Groups	Treat Group Category	Analysis Treatment Groups
Disposition	ITT	As randomized	High Dose, Low Dose, Overall	As enrolled
Baseline Characteristics, Medical History, Prior and Concomitant Medications	FAS	ATG-Day 1	High Dose, Low Dose, Overall	ATG- Day 1
Drug Exposure	Safety	ATG-All Dispensing	High Dose, Low Dose, All Low Dose, Any High Dose, Overall	ATG- Day 1

Table 1.SA Analysis Treatment Groups for Various Analyses P Version
Summary History (Continued)

			R	esected	Non- Resected (All High Dose)		
Analysis		Analysis Set	Analysis Treatment Groups	Treat Group Category	Analysis Treatment Groups		
Drug Con	npliance (wee	k 1)	Safety	ATG-Day 1	High Dose, Low Dose, Overall	ATG- Day 1	
	Primary	stool fat (Week 1 within group)	EAS-SF, EAS-SF- SUPP	ATG-Day 1	High Dose, Low Dose	ATG- Day 1	
Efficacy	Secondary	stool fat (Week 1 between group)	EAS-SF, EAS-SF- SUPP	ATG-Day 1	High Dose, Low Dose	NA	
		Stool Frequency/Stool Consistency/EPI Symptom Week 1	FAS	ATG-Day 1	High Dose, Low Dose	ATG- Day 1	
	Efficacy		Stool Frequency/Stool Consistency by visit	FAS	ATG- Dynamic	High Dose, Low Dose, Overall	ATG- Day 1
	Additional	PRO by visit (EPI/PAN 26/C30)	FAS	ATG- Dynamic	High Dose, Low Dose, Overall	ATG- Day 1	
		BMI/Weight by visit	FAS	ATG-All Dispensing	High Dose, Low Dose, All Low Dose, Any High Dose, Overall	ATG- Day 1	

Table 1.SA Analysis Treatment Groups for Various Analyses P Version
Summary History (Continued)

				R	esected	Non- Resected (All High Dose)
Analysis			Analysis Set	Analysis Treatment Groups	Treat Group Category	Analysis Treatment Groups
Efficacy Additional	Albumin and pre-albumin by visit	FAS	ATG-All Dispensing	High Dose, Low Dose, All Low Dose, Any High Dose, Overall	ATG- Day 1	
	Chemotherapy tolerability by visit	FAS	ATG-All Dispensing	High Dose, Low Dose, All Low Dose, Any High Dose, Overall	ATG- Day 1	
		AE/SAE in Week 1	Safety	ATG-Day 1	High Dose, Low Dose, Overall	ATG- Day 1
Safety		AE/SAE analyses (entire treatment period)	Safety	ATG- Dynamic	High Dose, Low Dose, Overall	NA
		All other AE/SAE analysis	Safety	ATG-All Dispensing	High Dose, Low Dose, All Low Dose, Any High Dose	ATG- Day 1
		Lab / Vital Signs	Safety	ATG-All Dispensing	High Dose, Low Dose, All Low Dose, Any High Dose	ATG- Day 1

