10.2.1.2 Exposure-Adjusted Incidence Rate (EAIR) for TEAE During the Entire Treatment Period

Dose escalation is allowed for subjects in resected population who meet dose escalation criteria on or after Week 1 visit. To adjust for potentially different exposure times between treatment groups, exposure-adjusted incidence rates will be provided based on ATG-Dynamic treatment group for resected population, and for Creon high dose cohort for non-resected population.

The exposure-adjusted incidence rate (EAIR) for a treatment group is defined as the number of subjects with a particular TEAE under that treatment group divided by the total exposure-time to that treatment group among subjects who had received that treatment. More specifically,

$$EAIR_i = \frac{n_i}{T_i} = \frac{n_i}{\sum t_{ij}},$$

where,

i = high dose, low dose;

j = 1, number of subjects who received treatment i,

 n_i : the number of subjects with the event when subject is under treatment i,

 t_{ii} : subject j's total exposure under treatment i, and

 T_i : the total exposure time for treatment *i*.

For subjects in resected population, to determine whether subject has the event under treatment i, ATG-dynamic group will be used. Namely, the treatment group will be determined based on the drug dispensed at prior study visit before the event occur. To calculate the total exposure time under treatment i for a subject, the drug dispensed at each dispensing visit will be considered, the total exposure time under high dose and/or

low dose will be calculated for each subject. E.g., if a subject has Day 1 dispensing = low dose, and Week 1 and subsequent visits dispensing = high dose, then for this subject:

- Low dose exposure time for this subject = date of Week 1 visit date of Day
- High dose exposure time for this subject = last date of study drug date of Week 1 visit +1.

Specifically, EAIR for TEAE during the entire treatment period will be summarized by treatment group as described below:

- 1. EAIR of TEAEs in descending order of overall incidence frequency by MedDRA PT in the entire treatment period
- 2. EAIR of serious TEAEs in descending order of overall incidence frequency by MedDRA PT in the entire treatment period
- 3. EAIR with drug-related (i.e., with reasonable possibility to be related to study drug) TEAEs by primary MedDRA SOC and PT
- 4. EAIR with drug-related (i.e., with reasonable possibility to be related to study drug) serious TEAEs by primary MedDRA SOC and PT

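### Severity tables and all-TEAE percentages stop at the Week 1 visit, so about 12 of 13 treatment weeks lack the severity tabulation that the Operations Manual promises

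*SAP*

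**What the plan says.** **Protocol side.** Operations Manual 4.2 plans the number and percentage of subjects with TEAEs by SOC and PT, counted from the start of study drug to 30 days after dosing. It adds: "The tabulation of the number of subjects with treatment-emergent adverse events by severity grade and relationship to study drug also will be provided". Neither commitment is limited to Week 1. Protocol 3.5 makes adverse events during participation or the 30-day follow-up the primary safety endpoint. Protocol 7.4 leaves the details of the safety analyses to the SAP.

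**SAP side.**
- Section 10.2.1.1 lists eight number-and-percentage summaries for the first week, defined as "Day 1 to Week 1 visit, inclusive". The first is "An overview of the number and percentage of subjects with TEAEs in the first week" and the last is "A summary of the number and percentage of subjects with TEAEs by primary MedDRA SOC, PT and maximum severity in the first week".
- Section 10.2.1.2 covers the whole treatment period with four exposure-adjusted incidence rate (EAIR) outputs. The first is "EAIR of TEAEs in descending order of overall incidence frequency by MedDRA PT in the entire treatment period". The others are serious TEAEs by PT, and drug-related and drug-related serious TEAEs by SOC and PT. None is graded by severity. The rates are to be given by ATG-Dynamic group for resected subjects "and for Creon high dose cohort for non-resected population".
- Section 10.2.1.3 gives a whole-period number and percentage, for TEAEs leading to discontinuation only.
- Section 10.2.2 plans subject listings.
- In Table 1 (Section 4.2), the row "AE/SAE analyses (entire treatment period" assigns ATG-Dynamic to resected subjects and NA to non-resected subjects. The next row, for all other AE/SAE analyses, assigns ATG-All Dispensing and ATG-Day 1 respectively.

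**The concern.** A report that follows the SAP exactly would not state how many subjects had any TEAE, a severe TEAE or a serious TEAE over the treatment period, and would grade events by severity only in the first week.

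For resected subjects that week is unusual in two ways. Protocol 5.3 says: "Subjects must not have started chemotherapy or radiation therapy from the time of the resection until after Week 1 of the study". The earliest dose escalation is at the Week 1 visit. Apart from that visit day, the only graded table therefore ends before any escalated dosing and, in subjects who follow Protocol 5.3, before any post-resection chemotherapy. Severe events arising later would appear only as listing lines or inside rates that do not separate severity.

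The Table 1 entry is a separate and smaller matter. A programmer cannot satisfy both the NA and the promise in 10.2.1.2.

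**Working it through.** **1. Outputs side by side**

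| Output | Operations Manual 4.2 | SAP, first week | SAP, entire treatment period |
|---|---|---|---|
| All TEAEs | number and percentage by SOC and PT | number and percentage by PT, and by SOC and PT | EAIR by PT |
| Any-TEAE overview | not itemised | number and percentage | none |
| Severity | number of subjects | number and percentage by SOC, PT and maximum severity | none |
| Relationship to drug | number of subjects | number and percentage, drug-related | EAIR by SOC and PT |
| Serious TEAEs | not itemised | number and percentage | EAIR by PT |
| Leading to discontinuation | not itemised | number and percentage | number and percentage |

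The severity row is empty for the whole period in both populations. SAP 10.2 sets a highest-severity counting rule, but no whole-period table uses it.

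**2. Time inputs**
- Treatment up to 91 days: Operations Manual 6.1. Its participation total reproduces: 56 + 91 + 30 = 177 days. 91 / 7 = 13 weeks.
- Week 1 visit on Day 8: SAP 3.1.
- Week 1 window of +2 days, so Day 8 to Day 10: Protocol 4.2.
- The visit day counts as first week: SAP 10.2.1.1.

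**3. Treatment time outside the first-week tables** = treatment days − day of Week 1 visit
- Visit on Day 8: 91 − 8 = 83 days; 83 / 7 = 11.9 weeks; 83 / 91 = 91%.
- Visit on Day 10: 91 − 10 = 81 days; 81 / 7 = 11.6 weeks; 81 / 91 = 89%.
- Assuming treatment ends at a Week 13 visit within its ±4-day window (87 to 95 days), the extremes are 87 − 10 = 77 days (11.0 weeks, 88.5%) and 95 − 8 = 87 days (12.4 weeks, 91.6%).

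The first-week tables thus cover 8 to 10 of 91 days (9% to 11%).

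**4. Is the departure declared?** SAP 1.0 refers to Section 12.0 for changes from the protocol's analyses. Section 12.0 deals only with type I error, so the restriction to Week 1 is not recorded there as a change.

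**The case against.** **The first-week focus has a reason.** Week 1 is the one period in which resected subjects are all on their starting dose. SAP 10.2.1.2 explains that later escalation makes exposure unequal, which is why it uses rates. That justifies adding the EAIRs. It does not explain leaving out severity, and SAP 10.2.1.3 already reports whole-period percentages despite dose switching. Non-resected subjects have no dose modification, so the reason does not reach them.

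**The list may not be exhaustive.** SAP 10.2.1 calls its three analyses the main ones, and Table 1 has a row for all other AE/SAE analyses with no Week 1 limit. That row assigns treatment groups; no SAP section defines a whole-period severity table or all-TEAE percentage under it.

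**Counts may be visible in the EAIR tables.** The numerator is a number of subjects, but for one event under one dose. A subject with several PTs is counted under each, so the PT counts do not add up to subjects with any TEAE, and severity is absent.

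**A reader might infer that safety after Week 1 is untabulated.** It is not: EAIRs, the discontinuation table and listings (including serious and fatal TEAEs and deaths) are planned.

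**A reader might infer from the NA that the non-resected cohort has no whole-period analysis, or that the NA causes the severity gap.** Neither follows. SAP 4.1 defines ATG-Dynamic for the resected regimen only, so the NA may mean only that this grouping does not apply. SAP 10.1 cites Table 1 for populations and treatment groups, not for which outputs exist. The severity gap comes from the output lists in 10.2.1.1 to 10.2.1.3.

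**The stakes are limited.** The study is Phase 4, is stated not to be for registration or labelling, and has no adverse events of special interest. This stands and limits the priority.

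**Conclusion.** The point holds as a reporting gap. Followed exactly, the SAP leaves the severity tabulation promised in Operations Manual 4.2 undelivered for 81 to 83 of up to 91 treatment days, about 12 of 13 weeks. Over the whole period it also gives no percentage of subjects with any, any severe or any serious TEAE. The size assumes 91 days of treatment and a Week 1 visit on Day 8 to Day 10. The documents give no incidence of severe events, so the number of subjects affected cannot be stated.

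The chemotherapy argument applies to resected subjects only. The Table 1 NA is a one-cell inconsistency to reconcile. Efficacy results, power and type I error are unaffected.

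**What to change.** In SAP 10.2.1, add number-and-percentage tables for the entire treatment period:
- (a) an overview of any, severe, serious and drug-related TEAEs;
- (b) TEAEs by SOC and PT;
- (c) TEAEs by SOC, PT and maximum severity.

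For resected subjects, use the ATG-All Dispensing groups that Table 1 already names for other AE analyses: High, Low, All Low and Any High. Footnote that the groups overlap, that the Day 1 Low group includes later escalators, and that Any High includes escalators' events from before the switch. For non-resected subjects, use the single cohort (ATG-Day 1). Repeating all eight first-week summaries is unnecessary, since 10.2.1.3 already covers discontinuations. Using Day 1 groups alone would put escalators' high-dose events in the low-dose column with no alternative grouping beside it.

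Reconcile the NA in Table 1 with 10.2.1.2, and keep the EAIR tables.

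Cost: SAP wording, a few more tables, and existing programs run over a longer window; no new data. The percentages will not be adjusted for exposure, which the EAIRs alongside address.

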10.2.1.2 Exposure-Adjusted Incidence Rate (EAIR) for TEAE During the Entire Treatment Period

Dose escalation is allowed for subjects in resected population who meet dose escalation criteria on or after Week 1 visit. To adjust for potentially different exposure times between treatment groups, exposure-adjusted incidence rates will be provided based on ATG-Dynamic treatment group for resected population, and for Creon high dose cohort for non-resected population.

The exposure-adjusted incidence rate (EAIR) for a treatment group is defined as the number of subjects with a particular TEAE under that treatment group divided by the total exposure-time to that treatment group among subjects who had received that treatment. More specifically,

$$EAIR_i = \frac{n_i}{T_i} = \frac{n_i}{\sum t_{ij}},$$

where,

i = high dose, low dose;

j = 1, number of subjects who received treatment i,

 n_i : the number of subjects with the event when subject is under treatment i,

 t_{ii} : subject j's total exposure under treatment i, and

 T_i : the total exposure time for treatment *i*.

For subjects in resected population, to determine whether subject has the event under treatment i, ATG-dynamic group will be used. Namely, the treatment group will be determined based on the drug dispensed at prior study visit before the event occur. To calculate the total exposure time under treatment i for a subject, the drug dispensed at each dispensing visit will be considered, the total exposure time under high dose and/or

low dose will be calculated for each subject. E.g., if a subject has Day 1 dispensing = low dose, and Week 1 and subsequent visits dispensing = high dose, then for this subject:

- Low dose exposure time for this subject = date of Week 1 visit date of Day
- High dose exposure time for this subject = last date of study drug date of Week 1 visit +1.

Specifically, EAIR for TEAE during the entire treatment period will be summarized by treatment group as described below:

- 1. EAIR of TEAEs in descending order of overall incidence frequency by MedDRA PT in the entire treatment period
- 2. EAIR of serious TEAEs in descending order of overall incidence frequency by MedDRA PT in the entire treatment period
- 3. EAIR with drug-related (i.e., with reasonable possibility to be related to study drug) TEAEs by primary MedDRA SOC and PT
- 4. EAIR with drug-related (i.e., with reasonable possibility to be related to study drug) serious TEAEs by primary MedDRA SOC and PT

10.2.1.3 Incidence Rate of TEAE Leading to Study Drug Discontinuation During the Entire Treatment Period

A summary of the number and percentage of subjects with TEAEs leading to discontinuation of study drug by primary MedDRA SOC and PT will be provided by treatment group (ATG-All dispensing) for resected population, and for high dose cohort in non-resected populations.

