2.5 Dose Modification

Dose modifications will be determined by a "dispensation score" calculated in EDC based on the responses to Questions 7, 8 and 10 from the EPI Symptom Questionnaire (Appendix D). The "dispensation score" will be then entered in IRT by the sites. Whether the subject needs dose modification will be determined by the "dispensation score" and IRT will then dispense the corresponding drug accordingly. The process will keep the site staff and the subjects blinded on whether the subject will be dose modified or not. The dose modification process including the details of the IRT dispensation score derivations are documented in the Study M16-142 Documentation of Key Decision dated 09 February 2020. The general dose modification rules are described as below.

Calculation of Total Score for Dose Modification:

The score for dose modification will be calculated by assigning the following values to each one of the responses to Questions 7, 8, and 10 in the EPI symptom questionnaire: none = 0, mild = 1, moderate = 2, severe = 3, very severe = 4. The total score for dose modification will be calculated as the sum of the responses to Questions 7, 8, and 10 within each visit. If none of the three questions are answered, the score will be noted as NULL.

The criteria for dose modification are described below:

- a. If current score = NULL, then maintain dose.
- b. If the previous score is NULL and the score for the current visit is available, then replace the previous score with the last available visit score as the previous score and follow the dose escalation criteria d) e) or f).
- c. If the Baseline visit score and all other visit scores prior to the present visit are NULL but the present visit score is available, then maintain dose.
- d. If current score <= 2, then maintain dose.
- e. If current score > 2 and there is less than 30% improvement from the previous score, i.e., current score > $(0.7 \times \text{previous score})$, then increase dose.

f. If current score > 2 and there is 30% or more improvement from the previous score i.e., current score <= $(0.7 \times \text{previous score})$, then maintain dose.

The subjects, site staffs and Abbvie site monitors will be blinded to the detailed dose modification criteria as well as the subject's dose medication status.

Resected Subjects

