The dose for resected subjects in the low dose cohort (12,000 USP units (Lipase) with meals/6,000 USP units (Lipase) with snacks) will be modified to the high dose (72,000 USP units (Lipase) with meals/36,000 USP units (Lipase) with snacks) at Week 1, 5, or 9 if the dose modification criteria defined above are met. Subjects randomized to the high dose cohort are not dose modified.

Only one dose modification will be permitted throughout the study. For subjects who have already experienced dose escalation, they will remain on the high dose level for the rest of the treatment duration, even if they continue to meet the dose escalation criteria in the subsequent visit(s). No further dose escalation is allowed.

Non-Resected Subjects

Non-resected subjects in the open-label population will continue to receive pancrelipase at a dose of 72,000 USP units (Lipase) with meals/36,000 USP units (Lipase) with snacks during the study; there will be no dose modification.

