4.1 Analysis Treatment Groups

The following analysis treatment groups will be used in different analyses:

- 1. Analysis Treatment Group Per Day 1 Dispensing (ATG-Day 1, Resected and Non-Resected Regimen): These treatment groups will be determined by the actual study drug the subjects were dispensed at Day 1 visit.
 - a. **High Dose Group:** Subjects who were dispensed the high dose (72,000 USP units (Lipase) with meals/36,000 USP units (Lipase) with snacks) at the Day 1 visit.
 - Low Dose Group: Subjects who were dispensed the low dose (12,000 USP units (Lipase) with meals/6,000 USP units (Lipase) with snacks) at the Day 1 visit.
- 2. Analysis Treatment Group Per All Dispensing (ATG-All Dispensing, Resected regimen only): The following treatment groups will be determined by the actual study drug the subjects were dispensed throughout the study.
 - a. **High Dose:** Subjects who were dispensed the high dose (72,000 USP units (Lipase) with meals/36,000 USP units (Lipase) with snacks) at the Day 1 visit.
 - b. Low Dose: Subjects who were dispensed the low dose (12,000 USP units (Lipase) with meals/6,000 USP units (Lipase) with snacks) at the Day 1visit.
 - c. All low Dose: Subjects who were dispensed the low dose (12,000 USP units (Lipase) with meals/6,000 USP units (Lipase) with snacks) at all visits.
 - d. **Any High Dose:** Subjects who was dispensed the high dose (72,000 USP units (Lipase) with meals/36,000 USP units (Lipase) with snacks) at any of the visits.
- 3. Analysis Treatment Group Dynamic (ATG-Dynamic) per visit (Week 1, Week 5, Week 9, Week 13, Resected regimen only): These treatment group will be defined based on study drug dispensed to the subjects at the prior visit. For example, the dynamic treatment group at Week 1 visit would be based on the study drug dispensed to the subjects at Day 1 visit, which can be identified after unblinding by the kit number that had been dispensed to the subjects at Day 1 visit.

- a. **High Dose Group:** Subjects who was dispensed the high dose (72,000 USP units (Lipase) with meals/36,000 USP units (Lipase) with snacks) at the prior visit.
- b. Low Dose Group: Subjects who was dispensed the low dose (12,000 USP units (Lipase) with meals/6,000 USP units (Lipase) with snacks) at the prior visit.

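### The whole-period exposure-adjusted AE rates pool Week 1 with later weeks, so Week 1 is over-represented in low-dose time and the two doses' rates can differ with no dose effect

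*SAP*

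**What the plan says.** SAP 10.2.1.2 defines the EAIR for a dose as the number of subjects with the event while on that dose, "divided by the total exposure-time to that treatment group among subjects who had received that treatment". Its stated purpose is the amount of exposure: "To adjust for potentially different exposure times between treatment groups, exposure-adjusted incidence rates will be provided based on ATG-Dynamic treatment group for resected population". Under ATG-Dynamic (SAP 4.1), "These treatment group will be defined based on study drug dispensed to the subjects at the prior visit". SAP Table 1 assigns this grouping to the row beginning "AE/SAE analyses (entire treatment period". No strata for study period or chemotherapy are given.

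Three other rules matter.

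- **Chemotherapy.** Protocol 5.3, for resected subjects: "Subjects must not have started chemotherapy or radiation therapy from the time of the resection until after Week 1 of the study". Chemotherapy is anticipated later, since its tolerability is summarised by visit through Week 13 (SAP 3.3 and 9.4.6).
- **Escalation.** Under SAP 2.5, low-dose subjects move to high dose "at Week 1, 5, or 9 if the dose modification criteria defined above are met". The trigger is "If current score > 2 and there is less than 30% improvement from the previous score", on the sum of three symptom items.
- **No downward move.** "Subjects randomized to the high dose cohort are not dose modified".

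The EAIR is one of three principal TEAE analyses in SAP 10.2.1. The first is a set of Week 1 TEAE tables (10.2.1.1), by Day 1 dose according to Table 1. The third covers TEAEs leading to discontinuation (10.2.1.3), by ATG-All Dispensing.

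**The concern.** Dividing by time on dose corrects for how much exposure each dose had. It does not correct for when that exposure occurred. A single rate per dose is a fair summary only if the background AE rate is the same throughout, or if both doses have the same mix of early and late time.

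Neither is assured here. The background can change after Week 1 because chemotherapy may then begin. The mix differs because every low-dose starter gives Week 1 to the low-dose denominator, while any escalated subject gives all later time to the high-dose denominator. The SAP's own worked example, a subject escalated at Week 1, has one week of low-dose time and the rest high-dose.

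At stake is the reading of the only whole-period dose summary that SAP 10.2.1 specifies for all, serious and drug-related TEAEs. A difference between its two rates could reflect study period rather than dose.

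**Working it through.** The EAIR section states no figure to reproduce, and the documents give no escalation share, chemotherapy uptake or AE rate. Those are assumptions below, shown over a range.

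**Inputs from the documents.** 36 resected subjects per cohort (SAP 2.4); 13 weeks of treatment (SAP 2.3), that is 1 week before the first escalation visit and 12 after; low-to-high moves only.

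**Assumptions.** *e* = share of low-dose starters escalated at Week 1; *k* = event rate after Week 1 divided by the Week 1 rate; no dose effect; no dropout; visits on target dates.

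**Step 1: person-weeks.**
Low = 36 × [1 + 12(1 − e)]; High = 36 × [1 + 12(1 + e)]. Each includes 36 person-weeks from Week 1.

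**Step 2: event-rate ratio (close to the SAP's EAIR for rare events).**
High/Low = {[1 + 12(1 + e)k] / [1 + 12(1 + e)]} ÷ {[1 + 12(1 − e)k] / [1 + 12(1 − e)]}

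For e = 0.5 and k = 3: High = 55/19 = 2.895; Low = 19/7 = 2.714; ratio 1.07.

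| e | Low / High person-weeks | Week 1 share, Low / High | Ratio, k = 2 | Ratio, k = 3 |
|---|---|---|---|---|
| 0 | 468 / 468 | 7.7% / 7.7% | 1.00 | 1.00 |
| 25% | 360 / 576 | 10.0% / 6.3% | 1.02 | 1.03 |
| 50% | 252 / 684 | 14.3% / 5.3% | 1.05 | 1.07 |
| 75% | 144 / 792 | 25.0% / 4.5% | 1.12 | 1.16 |
| 80% | 122.4 / 813.6 | 29.4% / 4.4% | 1.15 | 1.21 |
| 90% | 79.2 / 856.8 | 45.5% / 4.2% | 1.27 | 1.39 |

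The true ratio is 1.00 in every row. Three further cases:

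- If 20% of those still on low dose escalate at each of Weeks 1, 5 and 9, the Week 1 shares are 11.4% and 5.8%, and the ratios are 1.03 (k = 2) and 1.04 (k = 3).
- For an event that occurs only after Week 1, the ratio is (1 − High share)/(1 − Low share): 1.04 at e = 25%, 1.11 at 50%, 1.76 at 90%.
- If events cluster at the start (k = 0.3), the ratio falls below 1: at e = 50%, (6.4/19)/(2.8/7) = 0.84.

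**Step 3: the SAP's own estimator.** The SAP counts subjects with an event but does not stop exposure at the first event. Let a be the Week 1 rate per week, b = ka, and P(h) = 1 − exp(−h).

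- Low subjects with an event: 36e·P(a) + 36(1 − e)·P(a + 12b)
- High subjects with an event: 36·P(a + 12b) + 36e·P(12b)

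For e = 0.5, a = 0.10, k = 3: Low = 18 × 0.0952 + 18 × 0.9753 = 19.27 over 252 weeks = 0.0765. High = 36 × 0.9753 + 18 × 0.9727 = 52.62 over 684 weeks = 0.0769. The ratio is 1.01, against 1.07 in Step 2.

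| e | a per week | k = 1 | k = 2 | k = 3 |
|---|---|---|---|---|
| 50% | 0.005 | 1.00 | 1.05 | 1.07 |
| 50% | 0.05 | 0.98 | 1.03 | 1.04 |
| 50% | 0.10 | 0.97 | 1.00 | 1.01 |
| 90% | 0.005 | 0.99 | 1.25 | 1.37 |
| 90% | 0.05 | 0.89 | 1.08 | 1.15 |
| 90% | 0.10 | 0.79 | 0.91 | 0.93 |

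For rare events the two estimators agree. For common events the uncensored denominator pulls the ratio down, and it can cancel or reverse the period effect.

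**Step 4: does stratifying help?** A Mantel-Haenszel rate ratio with Week 1 and Weeks 2-13 as strata returns 1.00 at e = 25%, 50% and 90% with k = 2 and 3. With equal rates for both doses within each stratum, its numerator and denominator are identical.

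**The case against.** A reader might infer that low-dose exposure is concentrated in Week 1. The documents do not support that. Escalation is conditional, most of the rules in SAP 2.5 keep the dose unchanged, and it may happen as late as Week 9. Week 1 exceeds half of low-dose time only if 12(1 − e) < 1, that is if about 92% or more escalate at Week 1. At 50%, about 86% of low-dose time still falls after Week 1. A high share cannot be excluded, since three unchanged mild ratings (score 3, above both 2 and 0.7 × 3 = 2.1) meet the trigger, but nothing in the documents predicts it.

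A reader might also infer that chemotherapy events will be credited to high dose. Step 3 shows that this is not a general result.

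The other objections have force as well:

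- The Week 1 tables by Day 1 dose are chemotherapy-free by protocol and unaffected, so half of a period split already exists as percentages.
- AE listings carry both the Day 1 and the dynamic group, and two of the four EAIR tables are limited to drug-related events.
- No ratio, test or confidence interval between doses is planned for the EAIRs, and SAP 12.0 says the study is not for registration or labelling.
- Precision is low. At e = 50%, k = 3 and a = 0.02, about 10 low-dose and 28 high-dose subjects have the event. The 95% CI factor is exp(1.96 × √(1/9.8 + 1/28.1)), about 2, so a shift of 1.06 is well inside the noise.

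These points limit the size and consequence. They do not remove the mechanism. Two rates set side by side by dose invite comparison, no rate after Week 1 is planned, and Table 1's row for other AE analyses by ATG-All Dispensing has no all-TEAE summary specified for it in 10.2.1.

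**Conclusion.** The point holds in a limited form. Pooling Week 1 with later weeks over-represents Week 1 in low-dose time once anyone escalates, so the EAIRs can differ between doses with no dose effect.

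For rare events the High/Low ratio is about 1.02-1.07 if 25-50% escalate at Week 1 and the later rate is 2-3 times the Week 1 rate. With a 3-fold later rate it reaches about 1.2 or more only if about 80% or more escalate at Week 1. For common events the SAP's uncensored denominator can cancel or reverse the shift, so no direction can be stated in advance. The escalation share, rate ratio and event rates are assumptions.

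The primary endpoint and the Week 1 safety tables are not affected. This is a cheap improvement to one of the main safety tables.

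**What to change.** In SAP 10.2.1.2:

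1. Add EAIRs by dose for two periods: Day 1 to the Week 1 visit, and the Week 1 visit to last dose. Limit them to any, serious, drug-related and SOC-level TEAEs, and censor exposure at the first event.
2. If a whole-period dose contrast is reported, use a period-stratified (Mantel-Haenszel) rate ratio with its 95% CI.
3. State what the split does not remove. After Week 1, symptom-driven escalation moves symptomatic subjects into the high-dose rate, and chemotherapy start dates vary, so the later-period comparison remains confounded.
4. Add a whole-period TEAE summary by Day 1 dose. Provided Day 1 dispensing followed the randomisation, this is the comparison that randomisation protects.

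The cost is SAP wording, a split on visit dates and dispensing data that the EAIR program already uses, censoring at event onset, and a few more tables. No new data or protocol change is needed. The downside is sparse counts, which is why the split stops at SOC level.
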